CRF	Case Report Form
CSOC	Clinical Study Oversight Committee
DCC	Data Coordinating Center
DHHS	Department of Health and Human Services
DSMB	Data and Safety Monitoring Board
FFR	Federal Financial Report
FWA	Federalwide Assurance
GCP	Good Clinical Practice
HIPAA	Health Insurance Portability and Accountability Act
ICF	Informed Consent Form
ICH	International Conference on Harmonisation
IR	Inadequate responder
IRB	Institutional Review Board
ISM	Independent Safety Monitor
MOP	Manual of Procedures
MTX	Methotrexate
N	Number (typically refers to participants)
NIH	National Institutes of Health
OHRP	Office for Human Research Protections
OHSR	Office of Human Subjects Research
PI	Principal Investigator
QA	Quality Assurance
QC	Quality Control
RA	Rheumatoid arthritis
SAE	Serious Adverse Event/Serious Adverse Experience
SOP	Standard Operating Procedure
US	United States

[figure not shown]
Protocol Summary

Title	A pilot proof of concept study of the E ffects of A Administration of S CFAs in R heumatoid A rthritis I nadequate R esponders
Short Title	EASi-RAIR
Brief Summary	
This study is a pilot, proof of concept study to determine the effects of administering an oral SCFA supplement to RA patients with inadequate response to methotrexate. We will include up to 65 total participants to obtain the following sample sizes below. We will include up to 65 participants to obtain a sample size of at least 25 participants taking the oral supplement. We hypothesize that oral SCFA will change the participants' gut microbiome and regulatory immune responses. Additionally, we will include participants with inadequate response to methotrexate who do not want to take oral SCFA supplements but rather proceed directly to the next medication their treating physician suggests. We will include up to 30 participants to obtain a sample size of at least 20 participants. Clinical data to assess for adverse events, stool, urine samples and peripheral blood will be collected at baseline, 1 month, with an optional 2-month time-point, and an optional visit up to 12-months following the last visit after participants have started treatments with the next line of therapy. Fecal microbiome will be analyzed. Adaptive immune responses will be analyzed from participant blood samples.

Phase	Pilot proof of concept study
Objectives	
Primary objective:
 
 To determine whether oral SCFA supplementation in RA inadequate responders induces changes in the gut microbiome composition 
Key secondary objectives:
 
 To determine whether oral SCFA supplementation in RA inadequate responders induces changes in the peripheral Treg population To measure changes in adaptive immune response over time with oral supplementation of SCFA To measure changes in serum and fecal SCFA concentration with oral supplementation of SCFA To measure MTX and its metabolites in fecal and urine samples after oral SCFA supplementation To measure changes in the gut microbiome composition in methotrexate inadequate responders who do not want to take oral SCFA supplements. To measure changes in the gut microbiome composition in methotrexate inadequate responders after they initiate next line therapy (as prescribed by their treating physician)
Methodology	Open label pilot proof of concept study
Endpoint	
Primary endpoint:
 
 The primary endpoint will be an increase in microbiome alpha diversity from baseline visit 1 to visit 2 after SCFA supplementation. 
Important secondary endpoints:
 
 We will determine the changes to serum and fecal SCFA after SCFA supplementation and determine the changes in adaptive immune response including peripheral Treg cell populations.
Study Duration	Up to 4 years
Participant Duration	Up to 14 months

[figure not shown]
Duration of IP administration	Up to 2 months
Population	Any Rheumatoid Arthritis patient who is an inadequate responder to current RA treatment: 
• Age 18 years and above• Subjects not excluded based on gender, race or ethnicity, general health status, or geographic location
Study Sites	NYU Langone Health inpatient and outpatient sites, Bellevue Hospital
Number of participants	65 participants
Description of Study Agent/Procedure	Study agent is an oral SCFA supplement containing butyrate. It will be taken orally 1000mg three times a day with meals.
Key Procedures	Blood draws Stool collection Urine collection
Statistical Analysis	The primary endpoint of the trial is an increase in microbiome alpha diversity within subject pre- and post-SCFA supplementation at 1 month after initiation of treatment. According to our preliminary data in new-onset RA participants, SCFA supplementation leads to increase in alpha diversity with an effect size of 0.63. To be conservative, we will estimate an effect size of 0.60. A total of 25 participants will be needed to achieve an effect size of at least 0.60 while maintaining 80% power with a 0.05 type I error

Schematic of Study Design

Participants taking Oral SCFA Supplements

Participants Not Taking Oral SCFA Supplements

1 Key Roles

Principal Investigator

[name]
 Associate Professor of Medicine
 Director of the NYU – MiCRA
 Director of the NYU Psoriatic Arthritis Center (PAC)
 New York University Grossman School of Medicine
 [name]
 [name]
 Email: [contact]
 [contact]

Co-Investigators

[name], PhD

2 Introduction, Background Information and Scientific Rationale

2.1 Background Information and Relevant Literature

Methotrexate (MTX) is highly effective in about half of all rheumatoid arthritis (RA) patients¹⁻³ and remains the anchor drug for most of those who are recently diagnosed. It would therefore be beneficial to find a safe, effective, and inexpensive way to increase MTX response. A major mechanism by which MTX efficacy can be enhanced is through T regulatory cell (Treg) function⁴. The short chain fatty acid (SCFA) butyrate, a microbial fermentation product of certain gut microbes, has been shown to: i) induce a Treg immune response; and ii) promote changes in the gut microbiome in both murine models of inflammatory disease and in humans⁵⁻¹¹. Importantly, butyrate supplementation in patients with inflammatory disease has been shown to modify the gut microbial community towards an abundance of potentially beneficial butyrate producers¹¹, supporting the notion that oral butyrate may promote a more tolerogenic gut microbial niche in autoimmune conditions. Based on this

body of evidence, along with both our preliminary data and our published work showing that the baseline gut microbiome can be predictive of MTX responsiveness in new-onset RA (NORA) patients¹², we **hypothesize** that in RA patients with initial inadequate MTX response, the co-adjuvant administration of butyrate (along with MTX), will induce modifications in gut microbial communities that favor a regulatory adaptive immune response which can ultimately increase drug efficacy.

To our knowledge, the proposed study will constitute the first of its kind. There have been mixed results in small trials of probiotics and/or prebiotics in inducing immunoregulatory activity in healthy and diseased participants¹³⁻¹⁶ and in RA in particular¹⁷⁻¹⁹. We propose to circumvent the upstream mechanisms induced by the supplementation of probiotics and/or prebiotics and directly administer the gut microbial fermentation byproduct itself along with MTX to induce a more effective regulatory response in RA patients deemed refractory to the drug. If oral butyrate can induce even a modest increase in MTX efficacy, this strategy has the potential to allow patients to continue MTX monotherapy instead of unnecessarily switching to another DMARD. This would help reduce the dependence on alternative DMARDs, including targeted synthetic oral DMARDs and biologic DMARDs which are generally more prone to adverse events.

This is being submitted as a separate study from EASi-RA (i20-02068) because of the requirement for participants to have an inadequate response to MTX, while EASi-RA patients are new onset rheumatoid arthritis patients who are rheumatoid arthritis treatment naïve. The patients in this EASi-RAIR study are no longer “new-onset” rheumatoid arthritis compared to the patients in EASi-RA. Additionally, the primary outcomes in both studies are different, therefore necessitating implementation of a new IRB protocol.

Hypothesis

We **hypothesize** that in RA patients with inadequate MTX responses, the oral co-administration of butyrate along with MTX will induce modifications in gut microbial communities that favor a regulatory adaptive immune response that may ultimately increase MTX efficacy.

2.2 Name and Description of the Investigational Agent: Butyrate – a short chain fatty acid

This study is looking at the investigational agent short chain fatty acids (SCFA), and in particular, a four-carbon SCFA called butyrate. Oral butyrate and other oral SCFA mixtures can be found as dietary supplements in local health food shops and pharmacies and are not regulated by the FDA.

2.2.1 Preclinical Data

There is a substantial amount of published work suggesting that oral butyrate supplementation ameliorates inflammatory arthritis in murine models^{5,6}. Additionally, there have been a number of studies examining the effects of oral supplementation of SCFAs in humans in inflammatory diseases such as arthritis, MS and even the metabolic syndrome⁸. Cleophas, Ratter^{10,13,16,17}. Butyrate supplementation in patients with IBD alters the gut microbial community towards an abundance of butyrate producers¹¹. In particular, SCFA such as butyrate promotes T regulatory cell differentiation, production of IL10, and a shift from Th17 dominant phenotype to Treg phenotype⁵⁻¹⁰. In our lab we can see systemic changes in Treg circulation within one week in healthy volunteers following butyrate supplementation (unpublished data). Further, our lab has characterized the gut microbial composition in RA patients that are either responders or non-responders to MTX¹². One important mechanism of MTX is its role in promoting Treg function⁴. MTX responders have increased frequencies of regulatory T cells after MTX treatment whereas, nonresponders do not²⁰. Therefore, we propose that addition of SCFA to MTX therapy will induce more circulatory Tregs.

2.2.2 Clinical Data to Date

There is no available clinical research data to date on this product (Oral butyrate supplement from Biotics Research or Bodybio, Inc.). Please reference above for data on SCFA, and butyrate, in related studies.

2.2.3 Dose Rationale

Butyrate 1000 mg three times daily will be used in this study. This dose was based on doses found in the literature and over the counter general use guidelines that ranged from 1000mg – 6000 mg daily^{8,10,11}. In our ongoing study in NORA patients, the proposed dosing regimen is feasible, tolerable and promotes changes in gut microbiome diversity (unpublished data).

2.3 Rationale

MTX is effective in up to only 40-50% of all RA patients yet MTX monotherapy is an anchor drug for most RA patients. It would be beneficial to find a safe, effective and inexpensive oral agent that could increase MTX effectiveness. A major mechanism of MTX is by enhancing Treg function⁴. SCFA have been shown to induce a Treg immune response and induce changes in the gut microbiome in both murine models of inflammatory disease and human patients. Taken together, we propose that an oral SCFA-based supplement given to RA patients on a daily basis along with physician prescribed MTX will induce changes in gut microbial communities that favor a regulatory adaptive immune response. We will analyze gut microbial communities from patients prior to SCFA initiation and evaluate whether SCFA can shift a non-responder gut microbiome into a responder gut microbiome phenotype. We will also analyze blood samples from participants to characterize whether SCFA supplementation leads to increased production of T regulatory cells and regulatory cytokines. We will not have a placebo arm as this is a pilot proof of concept study.

2.4 Potential Risks & Benefits

2.4.1 Known Potential Risks

Risk of study supplement

Butyrate is a normal SCFA fermentation byproduct of our commensal gut microbiota. As such, no risks are expected other than those derived from ingestion of concentrated fatty acids, namely gastrointestinal intolerance (including pain and bloating) and (possibly) diarrhea. Subjects who experience any of these symptoms will be informed to contact their study doctor immediately at the telephone number provided by the PI.

The study team will work to minimize risks by monitoring subject experiences through the study and monitoring the withdrawal of subjects who experience certain risks or severe symptoms. This monitoring will be in the form of discussing with patients during their study visits and tracking of adverse events on case report forms and will be discussed with DSMB as required. There will not be no special monitoring in this case as this is a normal byproduct of gut microbiota and no serious risks are expected from the supplement.

Risks of all study related procedures

Blood draw: Possible side effects from drawing blood include: faintness, inflammation of the vein, pain, bruising, or bleeding at the site of puncture. There is also a slight possibility of infection.

Stool/Urine Sample Collection:

Potential contamination of surfaces or other people is the major risk of urine and stool collection procedure, which may transmit infectious diseases to animals and individuals.

Physical Examination

The physical examination will be performed by a qualified study physician as part of routine care. Minor discomfort may occur.

Loss of privacy and confidentiality: As with participation in any research study, there is always a risk that confidential or private information can be compromised. To minimize this risk, the study team will de-identify patient samples and replace identifying information, such as patient's name, with a bar code label that will not be associated with any date or identifiable information to the patient (for example birthday or street address). Samples will be stored in the PIs lab. Only [name] and his research team will have access to them.

2.4.2 Known Potential Benefits

The benefits of SCFA, particularly, butyrate, are currently unknown. Subjects will not benefit directly from the study. We hope the information gained will help us better understand the effects of SCFA in patients with RA.

3 Objectives and Purpose

- To determine whether SCFA alters the gut microbiome and to assess whether the changes in the gut microbiome alters systemic immune responses.
- Assess clinical responsiveness to oral supplementation of SCFA along with MTX in inadequate responders

3.1 Primary Objective

- To determine whether oral SCFA supplementation in RA inadequate responders induces changes in the gut microbiome composition

3.2 Secondary Objectives (if applicable)

- To determine whether oral SCFA supplementation in RA inadequate responders induces changes in the peripheral Treg population
- To measure changes in adaptive immune response over time with oral supplementation of SCFA
- To measure changes in serum and fecal SCFA concentration with oral supplementation of SCFA
- To measure MTX and its metabolites in fecal and urine samples after oral SCFA supplementation

4 Study Design and Endpoints

4.1 Description of Study Design

This study is a pilot proof of concept, open label study of the effects of oral SCFA supplementation in RA patients with an inadequate response to MTX. We will be enrolling all patients with RA who fulfill inclusion/exclusion criteria. This will be a single center study based in the NYU Langone hospitals and clinics as well as Bellevue Hospital which falls under its umbrella. Oral butyrate will be taken at 1000 mg three times daily with meals by RA patients who have active disease and are currently taking MTX at prescriber's recommended dose. There will be no dose escalation of the study supplement.

4.2 Study Endpoints

4.2.1 Primary Study Endpoints

The primary endpoint will be an increase in microbiome diversity (as measured by Shannon diversity index) from baseline visit 1 to visit 2 after SCFA supplementation with an effect size of at least 0.60.

4.2.2 Secondary Study Endpoints

We will determine changes in serum and fecal SCFA concentration over time to ensure that oral SCFA supplementation is localizing to the colon and/or peripheral circulation.

We will measure changes in adaptive immune response by flow cytometry, ELISA, T reg suppression assays and RNA-seq, over time with oral supplementation of SCFA with the hypothesis that oral SCFA supplementation will increase Treg and B regulatory cell responses over time.

We will measure changes in cytokine production over time with oral supplementation of SCFA with the hypothesis that oral SCFA supplementation will increase regulatory cytokine responses and decrease inflammatory cytokine responses.

Contingent upon observed changes in microbiome and/or changes in adaptive T and B cell populations, measurements of inflammatory transcripts may be performed on stored frozen PBMCs by measuring cell messenger RNA levels.

4.2.3 Exploratory Endpoints

We will determine the percentage change of gut microbiome composition from MTX-nonresponder (MTX-NR) phenotype to an MTX-responder (MTX-R) phenotype after SCFA supplementation. Our hypothesis is that oral SCFA supplementation will shift the microbiome to a more regulatory state and in parallel will shift the microbiome to a similar composition that is observed in patients who are MTX-R.

5 Study Enrollment and Withdrawal

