5.1 Inclusion Criteria

In order to be eligible to participate in this study, an individual must meet all of the following criteria:

1. Diagnosis of RA meeting 2010 ACR/EULAR for RA and/or treating MD diagnosis
2. Inadequate response to MTX per treating MD at maximum tolerated dose.
3. Able and willing to provide written informed consent prior to any study specific procedures
4. Age 18 years and above at time of enrollment
5. Subjects not excluded based on race or ethnicity

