9.1 Statistical and Analytical Plans (SAP)

The primary endpoint will be an increase in microbiome diversity (as measured by Shannon diversity index) from baseline visit 1 to visit 2 after SCFA supplementation with an effect size of at least 0.60. Our preliminary data of NORA patients reveals an increase in alpha diversity after butyrate supplementation with an effect size of 0.63 (Cohen's d) (unpublished data). Using this effect size for a two-tailed Wilcoxon signed-rank test, to be powered at 80% with a 0.05 type I error rate, we would need 23 participants to see a difference in pre-post treatment response in alpha diversity. However, to be more conservative, we will aim for 25 participants in order to achieve an effect size of at least 0.6 while maintaining 80% power with a 0.05 type I error. This number of participants is in line with previous studies^{11,21} and therefore should be sufficient for ours. These estimated sample sizes are based on before and after differences of the study group and we will not include a placebo group for the current proof-of-principle study. There will not be a formal SAP because due to the pilot nature of the proof of principle study.

Addition of a control group that do not take the SCFA supplement will not change the statistical analysis of the primary endpoint above since in the primary endpoint, the participants taking the SCFA supplement act as their

own controls. The additional control group will be used to explore secondary endpoints such as if there are gut microbial shifts after starting next line therapy as proposed by their treating physician.

It is expected that approximately 65 participants will be enrolled to produce at least 25 evaluable participants.

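### The exploratory MTX-responder phenotype endpoint names one direction of change only, so a one-way percentage would sit above zero in expectation even if SCFA did nothing

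*Combined protocol and SAP*

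**What the plan says.** Section 4.2.3 (Exploratory Endpoints) states: "We will determine the percentage change of gut microbiome composition from MTX-nonresponder (MTX-NR) phenotype to an MTX-responder (MTX-R) phenotype after SCFA supplementation". The accompanying hypothesis is that supplementation "will shift the microbiome to a similar composition that is observed in patients who are MTX-R". Section 2.3 (Rationale) gives the same single direction as an aim: to "evaluate whether SCFA can shift a non-responder gut microbiome into a responder gut microbiome phenotype".

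Entry is clinical. Section 5.1 requires "Inadequate response to MTX per treating MD at maximum tolerated dose" and sets no condition on the baseline microbiome.

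The documents do not give a classifier or score, a cut-off, a denominator, the follow-up visit, a count of moves from MTX-R to MTX-NR, a null value or a test for this endpoint. Section 9.1 says that there will be no formal SAP. It uses the group not taking SCFA for other questions, such as microbial shifts after next-line therapy. The Visit 1 schedule in section 7.3 has one stool collection and no repeat sample before treatment. On numbers, section 9.1 says: "It is expected that approximately 65 participants will be enrolled to produce at least 25 evaluable participants".

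**The concern.** Two stool samples from the same untreated person will not give identical profiles. Someone near a phenotype boundary can therefore be classed NR on one occasion and R on the next with nothing having changed. A percentage that records only NR-to-R moves starts at zero, cannot go negative, and picks up every such chance move in the hoped-for direction. Because entry is by clinical response, some participants may be classed R at baseline; they can move only in the direction that the endpoint does not name.

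A continuous score has the same problem if it is analysed only in people classed NR at baseline. They were selected partly for a low first reading, so their second reading tends to be higher.

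Section 2.3 presents the move toward a responder microbiome as something the study will evaluate. A positive percentage with nothing to calibrate it could be cited as evidence of that move when it reflects sampling variation.

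**Working it through.** **1. The plan's own figure.** No number is stated for this endpoint. The 25 comes from the primary endpoint in sections 9.1 and 9.2: a two-sided Wilcoxon signed-rank test, 80% power, alpha 0.05. Paired noncentral-t power with n multiplied by the Wilcoxon relative efficiency 3/π gives n = 23 at d = 0.63 (power 0.804) and n = 25 at d = 0.60 (power 0.801). Both match the plan.

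**2. Inputs.** From the documents: 25 evaluable SCFA participants. Assumed, because the documents give no values: the repeat-sample correlation r of an MTX-response score and the share p classed NR at baseline. The score is taken as standard normal at both visits with no treatment effect.

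**3. Formulas.** With cut-off c = Φ⁻¹(p) and NR meaning a score below c:
- chance that one participant goes NR to R: π = p − Φ₂(c, c; r)
- apparent shift among NR participants: π / p
- expected moves: 25π
- chance of at least one move: 1 − (1 − π)²⁵
- mean score rise in the baseline-NR subset: (1 − r)·φ(c) / p

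For p = 0.70 and r = 0.5: c = 0.524, φ(c) = 0.348 and π = 0.143. The shift is 0.143/0.70 = 20.5%, and the mean rise is 0.5 × 0.348/0.70 = 0.25 SD. For p = 0.90 and r = 0.9: c = 1.282, φ(c) = 0.1755 and π = 0.031. The shift is 0.0311/0.90 = 3.5%, and the mean rise is 0.1 × 0.1755/0.90 = 0.02 SD.

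**4. Results with no SCFA effect.**

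| NR at baseline | r | Shift, % of NR | Expected moves | P(at least one) | Mean rise in NR subset (SD) |
|---|---|---|---|---|---|
| 70% | 0.5 | 20.5 | 3.58 | 0.98 | 0.25 |
| 70% | 0.9 | 8.9 | 1.56 | 0.80 | 0.05 |
| 90% | 0.5 | 7.5 | 1.69 | 0.83 | 0.10 |
| 90% | 0.9 | 3.5 | 0.78 | 0.55 | 0.02 |
| 95% | 0.5 | 4.0 | 0.95 | 0.62 | 0.05 |
| 95% | 0.95 | 1.4 | 0.32 | 0.28 | 0.01 |

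Simulation of 20,000 trials per scenario over the 70% to 90% rows agrees: mean shift 3.4% to 20.6%, and at least one move in 54% to 98% of trials.

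**5. Cross-check with a flat switch rate.** If each NR participant switches with probability f, the chance of at least one move among n is 1 − (1 − f)ⁿ. For n = 25 this is 0.22 at f = 1%, 0.72 at 5%, 0.93 at 10% and 0.996 at 20%. For n = 10 it is 0.10, 0.40, 0.65 and 0.89. Reaching 95% needs f of at least 11.3% with 25 NR participants, or 25.9% with 10.

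**6. Counting both directions.** Assume each sample is misclassified with probability e, symmetrically, and nothing truly changes. Expected moves each way are 25·e(1 − e): 1.19 against 1.19 at e = 5%, 2.25 against 2.25 at 10%, and 4.0 against 4.0 at 20%. The expected net shift is 0. The net count is positive in 36%, 40% and 43% of trials, whereas at least one NR-to-R move appears in 70%, 91% and 99%.

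**7. Signed score in all SCFA takers.** In the no-effect simulations (3,000 runs per scenario), a two-sided signed-rank test on the change rejects in 4.1% to 5.5% of trials, close to the nominal 5%.

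**The case against.** The strongest reply is that section 4.2.3 contains no counting rule. It speaks of change in composition and of similarity to the MTX-R profile, which reads naturally as a continuous measure. It does not say that participants are dichotomised, that reverse moves are dropped, or that analysis is limited to a baseline-NR subset. The NR phenotype may simply describe where a clinically non-responding group starts. On that reading, a signed change in all SCFA takers is not biased by noise. This stands: the bias is conditional on a one-way tally or a baseline-NR subset, and the text permits those readings without requiring them.

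The size also rests on invented inputs. The documents give no repeatability and no NR share, and with nearly everyone classed NR or very repeatable samples the apparent shift falls to 1% or 2%. That stands too. In the other direction, if only half were NR the cut-off would lie nearer the middle, and the same model gives a mean shift of 14% to 33%.

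A reader might go further and infer that chance alone will almost always produce a shift, or that the endpoint cannot discriminate. The documents support neither. The chance of at least one move ranges from 0.10 to 0.996 over switch rates of 1% to 20% and 10 to 25 NR participants, and the plan does not treat one mover as success. A percentage far above what noise would give would still stand out. What is missing is the value to compare it with.

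Finally, the endpoint is exploratory and drives no decision. That limits the importance of the point, but the correction is nearly free.

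**Conclusion.** The point holds in conditional form. The endpoint is written in one direction, has no null value or comparator tied to it, and applies to people not selected on microbiome phenotype. Reported as an NR-to-R percentage, or as a score change among those classed NR at baseline, it is positive in expectation for any imperfect repeatability, with no SCFA effect needed. Under the assumed values in the working, the size is about 3% to 21% of NR participants, or 0.02 to 0.25 SD on a continuous score in that subset.

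A continuous signed measure in all SCFA participants would escape the bias, and the sponsor may have intended one; the text does not settle it. The consequence is confined to the interpretation of one exploratory result. The regulatory-immune part of the trial's hypothesis is addressed by the secondary endpoints in section 4.2.2, which this point does not touch.

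**What to change.** Amend section 4.2.3 to state that:
- all SCFA participants with paired Visit 1 and Visit 2 stool are included, whatever their baseline phenotype;
- each sample is scored with one MTX-response microbiome score, named in the protocol and fixed, with its cut-off, before the paired data are examined;
- the signed within-person change in score is tested with a two-sided Wilcoxon signed-rank test, the test already used for the primary endpoint;
- NR-to-R and R-to-NR moves are tabulated together, and the one-way percentage is not read alone as an SCFA effect.

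An exact McNemar test on the two-way table is optional. It has little power at 25 pairs (under no effect it rejects in at most about 2% of trials), so the score change should carry the inference. The group not taking SCFA does not replace this fix: it is self-selected and moves to next-line therapy, so it is not a clean measure of natural variation.

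The cost is a wording change and a few lines of analysis code, with no new samples, visits or participants. The downside is that the reported shift will look smaller than a one-way percentage would.
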